3.3 Exposure definition and measurement

To identify users of oral glucose lowering medications, including rosiglitazone, we will use the Aarhus University Prescription Database (AUPD)¹⁶ in Denmark and the General Practice Research Database (GPRD) in the UK.¹⁷ The AUPD tracks prescription dispensations, while the GPRD records prescriptions issued by physicians. Antidiabetic medications are available by prescription only in both countries.

We will identify patients with *two or more* prescriptions for oral glucose lowering drugs redeemed (in Denmark) or issued (in UK) between 1 January 2000 and 1 January 2011. Because dispensed prescriptions contain personal identifiers, we will be able to determine the number of unique users of each oral glucose lowering drug or their combinations. Currently, AUPD contains data on approximately 2,400, while GPRD has data on approximately 20,000 users of rosiglitazone preparations.

Based on recorded prescription dates, we will examine the patterns of oral glucose lowering drug use during the study period. A person will be considered a switcher once they have received two or more prescriptions for a new therapy. Users will be classified into several categories (not all drug combinations listed below may exist in the actual data):

- Those who receive rosiglitazone monotherapy as the first oral glucose lowering drug;

- Those who use oral glucose lowering drugs other than rosiglitazone (classified by type of drug);
- Those who switch from oral glucose lowering drugs other than rosiglitazone to rosiglitazone;
- Those who switch from rosiglitazone to an alternative oral glucose lowering drug. This group may include people who received alternative oral glucose lowering drugs before rosiglitazone use;
- Those in whom rosiglitazone is added to a prior alternative therapy;
- Those in whom an alternative oral glucose lowering drugs is added to rosiglitazone therapy.

List of medications, with codes used to identify them, appears in Appendix 1.

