To more clearly display time trends and the influence of the milestones that separate the time periods, we will create smoothed plots of the four parameters listed in the bullets above. We will define a window of length four months, and calculate each of the four parameters in that window, beginning in the first four months of 2000 (January, February, March, and April). We will plot the values of the four parameters at the midpoint of the window (1 March 2000). We will then slide the window one month forward and recalculate all four parameters in that window (February, March, April, and May of 2000). Data from January of 2000 falls out of the window and data from May of 2000 enters the window). We will plot the values of the four points at the midpoint of the window (1 April 2000). We will continue to slide the four-month window along the time axis until the end of the study period, calculating the parameters and plotting them at the midpoint of each window. The result will be a smoothed plot of trends in the parameters. We expect, for example, that the number of prescriptions for rosiglitazone will not exceed 0 until the first window that includes August 2000 appears. The number of prescriptions for rosiglitazone will likely increase, then reach a steady state, then decrease with the first milestone (May 2007). We will depict these milestone events on the graph, which will clearly display the correspondence between changes in the parameters and the milestone events.

This method of smoothing the results depicts trends without imposing a model on the data. A model embeds assumptions, such as the expected changes in trends at the milestones, which can become a self-fulfilling prophecy. It is important to begin the analysis without a model. If the smoothed data suggest that models of these results would be productive, and the modelling results would be useful, then we will fit models of the appropriate form. We expect these models will require regression splines, with knots (nodes) at the milestone dates. Such models would allow us to calculate, for example, the rate of change in number of prescriptions or proportion of diabetics receiving prescriptions within time periods. The model would also allow a quantitative comparison of the change in proportion in Denmark versus the UK, as a measure of homogeneity of the response in Europe to the milestone events.

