type2	250.01-250.05; 250.08	E11.2-E11.8
Any tumor	140-194	C00-C75
Leukemia	204-207	C91-C95
Lymphoma	200-203; 275.59	C81-C85; C88; C90; C96
Moderate to severe liver disease	070.00; 070.02; 070.04; 070.06; 070.08; 573.00; 456.00-456.09	B15.0; B16.0; B16.2; B19.0; K70.4; K72; K76.6; I85
Metastatic solid tumor	195-198; 199	C76-C80
AIDS	079.83	B21-B24

Anatomical Therapeutic Chemical (ATC) codes used to abstract the Aarhus University Prescription Database

Drug	ATC code
Drugs used in diabetes	A10
Insulins and analogues for injection, fast-acting	A10AB
Insulins and analogues for injection, intermediate-acting	A10AC
Insulins and analogues for injection, intermediate-acting combined with fast-acting	A10AD
Insulins and analogues for injection, long-acting	A10AE
Insulins and analogues for inhalation	A10AF
Rosiglitazone preparations	A10BG02 rosiglitazone A10BD03 rosiglitazone+metformin A10BD04 rosiglitazone+glimepiride
Biguanides	A10BA
Sulfonamides, urea derivatives	A10BB
Sulfonamides (heterocyclic)	A10BC
Combinations of oral blood glucose lowering drugs	A10BD (except A10BD03 and A10BD04)
Thiazolidinediones other than rosiglitazone	A10BG03 (pioglitazone)
Alpha glucosidase inhibitors	A10BF
Dipeptidyl peptidase 4 (DPP-4) inhibitors	A10BH
Other blood glucose lowering drugs, excl. insulins	A10BX
Lipid-lowering drugs including statins	C10A
Antihypertensive agents	C07 (beta blockers) C08 (calcium channel blockers) C09, C09 (ACE-inhibitors and angiotensin blockers)
Diuretics (loop, potassium sparing, thiazide)	C03
Nitrates	C01DA
Antiplatelet agents (anti-thrombotic)	B01A

ATC classification: http://www.whocc.no/atc_ddd_index/

Codes used to identify laboratory tests according to the International Union of Pure and Applied Chemistry (IUPAC)

Test	IUPAC codes
Fasting blood glucose	ASS00203, ASS00204, DNK35842, NPU02193, NPU02195, NPU08509, NPU08972, NPU22069
HbA1c	NPU02307, NPU03835
Haemoglobin (anaemia)	NPU02319, AAA00359, AAA00137, AAA00115
Alanintransaminase	DNK05051, NPU19651
Albumin/creatinine ratio (urine)	ASS00023, ASS00024, ASS00194, AAA00760, DNK05289, NPU03918, NPU03929, 10913
Serum creatinine	NPU18016, NPU01807
Total cholesterol	NPU01566
LDL cholesterol	NPU01568, NPU10171
HDL cholesterol	NPU01567, NPU10157
Triglycerides	NPU03620

IUPAC codes: <http://www.sst.dk/NPU>

Diagnostic codes used to abstract the General Practice Research Database**Diabetes (includes both non-specific and Type II)**

13AB.00 DIABETIC LIPID LOWERING DIET

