 G822.00 Embolism and thrombosis of the vena cava
 G80y.11 Phlebitis and/or thrombophlebitis of iliac vein
 G80y200 Phlebitis of the external iliac vein
 G80y400 Thrombophlebitis of the common iliac vein
 G80y600 Thrombophlebitis of the external iliac vein
 G80y800 Phlebitis and thrombophlebitis of the iliac vein
 G801.00 Deep vein phlebitis and thrombophlebitis of the leg
 G801000 Phlebitis of the femoral vein
 G801100 Phlebitis of the popliteal vein
 G801200 Phlebitis of the anterior tibial vein
 G801400 Phlebitis of the posterior tibial vein
 G801500 Deep vein phlebitis of the leg unspecified
 G801600 Thrombophlebitis of the femoral vein
 G801700 Thrombophlebitis of the popliteal vein
 G801A00 Thrombophlebitis of the posterior tibial vein
 G801B00 Deep vein thrombophlebitis of the leg unspecified
 G801z00 Deep vein phlebitis and thrombophlebitis of the leg NOS
 G401.00 Pulmonary embolism
 G401.12 Pulmonary embolus

Oral Hypoglycemic Agents

ORAL ANTIDIABETICS_sulfonylureas

2108 Acetohexamide
2110 Tolazamide
2115 Tolbutamide
2116 Glibenclamide (aka Glyburide)
2133 Glibornuride
2139 Glipizide
2148 Gliclazide
2159 Glimepiride
2140 Gliquidone
2120 Chlorpropamide

ORAL ANTIDIABETICS_Acarbose

2157 Acarbose

ORAL ANTIDIABETICS_Biguanides

2122 Metformin

ORAL ANTIDIABETICS_Glinides

2161 Repaglinide
2165 Nateglinide

Dipeptidyl peptidase 4 inhibitors

1079 SITAGLIPTIN

Oral Antidiabetics_PPAR agonists

2163 ROSIGLITAZONE
2167 ROSIGLITAZONE AND METFORMIN
2160 TROGLITAZONE
2162 PIOGLITAZONE
51050 ROSIGLITAZONE + GLIMEPIRIDE
51067 PIOGLITAZONE / METFORMIN

Insulin

2103 INSULIN
2109 (CZI CRYSTALLIN ZINC INSULIN
2111 INSULIN ZINC SUSPENSION
2112 INSULIN ZINC SUSPENSION EXTENDED
2125 DEPOT-INSULIN CS
2128 GLOBIN ZINC INSULIN INJECTION
2129 KOMB-INSULIN
2136 INSULIN NOVO-RAPITARD
2138 INSULIN LEO
2141 LONG INSULIN
2144 INSULIN CS

2151 INSULIN HUM NPH W ISOPHANE
 2154 INSULIN HUM NPH W NEUTRAL/SOLUBLE

 2158 PRO-HUMAN INSULIN LISPRO
 16221 INSULINS & ORAL ANTIDIABETIC AGENTS
 51007 INSULIN PORC ZINK / LENTE SEMILENTE
 51008 INSULIN BEEF
 02170 HUMALOG

Statins

1214 PRAVASTATIN
 1217 FLUVASTATIN
 1218 ATORVASTATIN
 1219 CERIVASTATIN
 1220 SIMVASTATIN
 1221 ROSUVASTATIN CALCIUM
 1222 EZETIMIBE + SIMVASTATIN
 19103 SIMVASTATIN
 1212 LOVASTATIN

Antihypertensive Agents

ACE-inhibitors_P

2202 IMIDAPRIL HCL
 4555 CAPTOPRIL
 4559 ENALAPRIL
 4566 LISINOPRIL
 4574 PERINDOPRIL
 4575 RAMIPRIL
 4578 CILAZAPRIL
 4580 FOSINOPRIL
 4592 MOEXIPRIL
 4609 TRANDOLAPRIL

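### The UK glucose-lowering drug list goes by substance and the Danish list by class, so UK moves from rosiglitazone to an unlisted drug are misclassified and have no switch baseline

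*Protocol*

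**What the plan says.** Section 3.3 of the protocol makes the appendix the operative definition of exposure: "List of medications, with codes used to identify them, appears in Appendix 1".

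For Denmark, Appendix 1 starts from the whole ATC group A10, "Drugs used in diabetes". It then lists whole classes, among them "Dipeptidyl peptidase 4 (DPP-4) inhibitors" (A10BH), "Combinations of oral blood glucose lowering drugs" (A10BD, less the two rosiglitazone codes), alpha-glucosidase inhibitors (A10BF) and "Other blood glucose lowering drugs, excl. insulins" (A10BX).

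For the UK, Appendix 1 names individual substances. The DPP-4 heading contains only "1079 SITAGLIPTIN". There is one oral combination without rosiglitazone (pioglitazone with metformin), acarbose alone, two glinides, and no residual entry. One broad code, "16221 INSULINS & ORAL ANTIDIABETIC AGENTS", is filed under Insulin without explanation.

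Section 3.6.1 counts a person as a switcher after at least two prescriptions for a new therapy. It also lists cessation of all antidiabetic drugs as a form of switching and reports discontinuation by period. Section 3.6.3 sets the baseline for patient-level endpoints at the date of a switch or addition shown by a new dispensation or issue, and section 3.6.4 compares laboratory values before and after that date. If models are fitted, section 3.6.1 foresees a "quantitative comparison of the change in proportion in Denmark versus the UK, as a measure of homogeneity of the response in Europe".

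**The concern.** The drug that a patient takes after rosiglitazone decides whether the patient is a switcher, whether there is a switch date, and whether the patient enters the acute-reaction and laboratory analyses of switches away from rosiglitazone. If the two countries recognise different sets of destination drugs, the same patient history can be classified differently in each. The misclassification can run only one way by country: a drug outside the UK list is invisible in the UK but visible in Denmark if it falls under A10. The UK is also the larger source, with about 20,000 of 22,400 rosiglitazone users (20,000 + 2,400), or 89%.

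**Working it through.** The protocol states no figure on this point, so there is none to reproduce. The check compares the two lists and then follows one patient through the rules.

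**Step 1: the lists (Appendix 1).**

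| Group | Denmark | UK |
|---|---|---|
| DPP-4 inhibitors | A10BH, whole class | sitagliptin |
| Oral combinations without rosiglitazone | A10BD, less A10BD03 and A10BD04 | pioglitazone with metformin |
| Alpha-glucosidase inhibitors | A10BF, whole class | acarbose |
| Other non-insulin drugs | A10BX, whole class | no residual entry (repaglinide and nateglinide stand under a glinide heading) |
| Rosiglitazone preparations | three codes | the same three preparations |

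The rosiglitazone entries match. The difference lies in the alternatives.

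**Step 2: a patient who leaves rosiglitazone for a drug in one of these groups that has no UK code.**

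- Denmark: the new drug falls under A10. After two dispensations the patient is a switcher, with a date, a 45-day window (3.6.3) and before/after laboratory values (3.6.4).
- UK, no other listed drug: there is no further record of any listed drug, so in 3.6.1 the patient appears to have stopped all treatment.
- UK, another listed drug continues: in 3.6.1 the patient appears only to have dropped rosiglitazone.
- Both UK cases: no listed new therapy is issued, so this move gives no switch baseline, no 45-day window and no laboratory comparison.

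**Step 3: illustrative size.** Let u be the share of all UK rosiglitazone users who move to an unlisted drug, and f the share of those with no other listed drug. The protocol gives neither, so both are assumptions.

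- Without a switch baseline for the move: 20,000 × u
- Wrongly shown as having stopped: 20,000 × u × f

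| u | No switch baseline | Shown as stopped, f = 25% to 100% |
|---|---|---|
| 1% | 20,000 × 0.01 = 200 | 50 to 200 |
| 5% | 20,000 × 0.05 = 1,000 | 250 to 1,000 |
| 10% | 20,000 × 0.10 = 2,000 | 500 to 2,000 |

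The remaining 20,000 × u × (1 − f) appear only to have dropped rosiglitazone. For the same drugs the Danish figure is 0, and with matched lists u = 0 in the UK as well.

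**Step 4: the rosiglitazone share in 3.6.1.** The share is R / N, where R is persons with rosiglitazone and N is persons with any antidiabetic drug. R is fully coded in both countries. If d persons in a period take only unlisted drugs, the UK calculation gives R / (N − d), which is too high. The documents give neither N nor d.

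**The case against.** The strongest reply is that no missing drug has been shown. A substance list is narrower in practice only if other agents were prescribed in GPRD practices during the study period, and the protocol names none. Nor does it say whether an entry such as sitagliptin also covers combination products. This stands as a limit on size: the gap may be small, or even empty. It does not remove the point, because the protocol nowhere says that the UK list was checked against the Danish classes.

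Several stronger readings are tempting but are not supported:

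- **That these UK patients are lost from all switch analyses.** Section 3.6.1 counts complete cessation as a form of switching and reports discontinuation, so there they are misclassified, not lost. (That item sits awkwardly with the rule of two prescriptions for a new therapy, and the two need to be reconciled.) Only 3.6.3 and 3.6.4 lack them. Missing some destinations there reduces numbers and narrows scope; it does not by itself bias the before/after comparison in those retained.
- **That the Denmark–UK comparison is invalid.** It is conditional on models being fitted. If it is applied to the rosiglitazone share, the numerator is complete in both countries and only the denominator is exposed.
- **That the number affected can be computed by applying a share of leavers to all 20,000 users.** That would assume every user left rosiglitazone under observation.
- **That code 16221 inflates off-label insulin use.** The protocol does not say what the code covers or whether any prescription carries it. An off-label flag also needs such a prescription between the first and last rosiglitazone prescription (3.4.2).
- **That the error grows in later periods.** This would need dates of use of unlisted drugs, which the protocol does not give.

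**Conclusion.** The point holds as a difference between countries in how exposure is defined. It is fixed in Appendix 1 and can misclassify moves to unlisted drugs in the UK but not in Denmark. The affected results are the UK switching and discontinuation figures in 3.6.1, the UK counts of alternative drugs, the denominator of the UK rosiglitazone share, and the set of UK patients available as switchers from rosiglitazone in 3.6.3 and 3.6.4. Counts of rosiglitazone users and prescriptions are not affected, and the destination codes for switches to rosiglitazone are complete.

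The size is unknown. The range of 200 to 2,000 patients rests on an assumed 1% to 10% of about 20,000 UK users and is not an estimate. What code 16221 covers remains an open question to be settled, not a demonstrated error.

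**What to change.** Before extraction, search the GPRD drug dictionary for every product that maps to the Danish A10B classes and add the missing codes to the UK list in Appendix 1. Put both countries' codes in one class-level crosswalk, and freeze it before switch status is derived. If the search finds no missing products, record that in the protocol.

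For code 16221, list the products it contains and assign each one to insulin or to oral agents. Section 6.2 says that the Drug File has a specific code for each commercial preparation, so this can be done at product level.

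The cost is a dictionary search and a small amount of programming; no new data are needed.

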3.4 Endpoints

All codes relevant to abstracting diagnostic, drug, and laboratory data appear in Appendix 1.

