3.4.2 Off-label use

These outcomes will be ascertained using AUPD or the Danish National Registry of Patients in Denmark and using the GPRD's Event File or Drug File in the UK. Off-label use will be defined as prescription of rosiglitazone dispensed by/issued to:

- Patients aged 16 years or younger at the time of any rosiglitazone prescription;
- Patient with concomitant use of insulin, defined as at least one prescription for insulin in between the first and last prescription for rosiglitazone²;
- Patients diagnosed with type 1 diabetes mellitus;

- Women with gestational diabetes without evidence of pre-gestational diabetes (UK only);
- Women with polycystic ovary syndrome (UK only)

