6.2 United Kingdom

The GPRD data are recorded using multiple data screens or files. These include the registration file, the drug file, the event file, the laboratory file, and files containing additional clinical details:

Registration File This file contains information regarding the registration status of each covered patient. Besides unique identification numbers for each individual, family, and practice, this file includes year of birth, gender, date of registration with the current general practice, most recent registration status (permanent, transferred out, died), and date of death or departure from the practice including reason for departure (where applicable).

Drug File This file contains detailed information on all drugs prescribed by the GP. Drugs are coded with the Multilex coding system, with a specific code for each commercial preparation. Details include the date of each drug prescription, the precise drug formulation and strength, the quantity and the dosing instructions of drug prescribed. In addition, the indication for treatment is required for all new courses of therapy. This classification of indication is done by cross-referencing prescriptions against medical events on the same date. It is worth noting that when patients are initially seen by consultants or in hospital, future drug therapy is directed through the GP and is thus captured by the database.

Event File This file contains all clinically relevant patient diagnoses along with the date of the event. Because the GP is the primary care giver for all patients in the National Health Service, all consultants are required to send a letter to the GP whenever a patient is seen in hospital or by an outpatient specialist, describing the relevant clinical events and final diagnoses. In addition to usual care in the GP office, GPs are required to enter all diagnoses resulting from hospitalizations, consultations, or emergency medical care. Diagnoses and events are coded using the READ code.

Additional Clinical Details File This file contains patient general health/life information such as blood pressure, height, weight, smoking status, alcohol use, cervical smears, and medical procedures. While the GPs are not required to update all of these data fields, information on characteristics such as height, weight, and smoking have been used repeatedly and are available on greater than 70% of the population.

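### The UK insulin code list includes one code whose label also covers oral drugs, so a record under it does not by itself establish insulin co-use

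*Protocol*

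**What the plan says.** Section 3.4.2 of the protocol lists the forms of off-label use to be counted. One of them reads: "Patient with concomitant use of insulin, defined as at least one prescription for insulin in between the first and last prescription for rosiglitazone". For the UK this is to be ascertained "using the GPRD's Event File or Drug File in the UK".

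Section 3.4 makes the appendix the operative code list: "All codes relevant to abstracting diagnostic, drug, and laboratory data appear in Appendix 1". In Appendix 1, the GPRD drug codes have an Insulin block of 18 entries. One of these is "16221 INSULINS & ORAL ANTIDIABETIC AGENTS". None of the other 17 labels mentions oral drugs. The code does not appear in the separate block of oral hypoglycaemic agents.

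The Danish counterpart in Appendix 1 identifies insulin by ATC groups A10AB to A10AF. Each is labelled as insulin only, the first being "Insulins and analogues for injection, fast-acting".

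Nothing in the protocol excludes 16221, limits it to records of insulin products, or asks for a second or confirming insulin record.

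**The concern.** A code list that defines insulin use should contain only codes that establish insulin use. The label of 16221 names insulins and oral antidiabetic drugs together, so a record under it leaves open which of the two was prescribed. The case rule offers no protection, because one record in the window is enough. The people being classified are all on oral glucose-lowering treatment, so if oral products are filed under this code, this is a group in which such records could occur.

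Off-label use is one of the study's specific aims, and section 3.6.2 promises the proportions by country and over time. Any false cases from this code would arise in the UK only. They would raise the UK insulin co-use proportion and add to any gap between the UK and Denmark for a reason unrelated to prescribing.

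**Working it through.** The plan attaches no figure to this point, so there is none to reproduce. The check is whether the misclassification follows from the text, and what would bound its size.

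**Does it follow from the text?**

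1. Section 3.4 sends the analyst to Appendix 1 for every drug code.
2. Appendix 1 puts 16221 in the UK insulin block, so a 16221 record is read as an insulin prescription.
3. Section 3.4.2 requires at least one such prescription between the first and last rosiglitazone prescriptions.
4. A user with one 16221 record in that window, and no other insulin code, is therefore classified as off-label whatever the product was.
5. The same patient in Denmark would need a record in A10AB to A10AF, all insulin-only, so this route does not exist there.

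**What limits it?**

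- Appendix 1 gives oral drugs their own codes, for example "2122 Metformin". Counting the UK entries gives 10 sulfonylureas + 1 acarbose + 1 biguanide + 2 glinides + 1 DPP-4 inhibitor + 6 glitazone entries (combinations included) = 21 codes. Prescriptions for those drugs would be expected under those codes.
- Section 6.2 states: "Drugs are coded with the Multilex coding system, with a specific code for each commercial preparation". Taken at face value, this leaves little room for ordinary oral prescriptions under a group label.
- Against that, the drug codes in Appendix 1 are mostly labelled by substance or group rather than by commercial product, so the statement in section 6.2 does not show what 16221 contains.
- The UK oral list is also narrower than the Danish one. It names a single DPP-4 inhibitor and has no residual class, while Denmark takes all of A10BH and A10BX. Whether any unlisted oral product is filed under 16221 is not stated.

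**Scale, under an assumed share**

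Let *s* be the share of UK rosiglitazone users who have an oral-drug record under 16221 in the window and no true insulin record there. The protocol gives no value for *s*. With about 20,000 UK users (section 3.3):

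false cases = 20,000 × *s*; added percentage points = 100 × *s*.

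| Assumed *s* | False cases | Added to UK proportion |
|---|---|---|
| 0% | 0 | 0 points |
| 0.1% | 20 | 0.1 point |
| 1% | 200 | 1 point |
| 5% | 1,000 | 5 points |

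The rows show how the error would scale. They are not estimates, and the first row is fully compatible with the documents.

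**The case against.** The strongest reply is that the mechanism is assumed. No part of the protocol shows an oral-drug prescription filed under 16221, and the separate oral codes together with the coding statement in section 6.2 suggest there may be few or none. The label also begins with insulins. It could be a class heading with no prescriptions, a residual code, or a record of combined insulin and oral treatment. In the last case, counting it as insulin would be correct. A broad code may also have been included on purpose, to catch insulin products that the other 17 entries miss. Finally, proportions are reported by country, so the UK figure is not weighted into a pooled result, and the two countries already differ in recording issued versus dispensed prescriptions.

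Most of this stands. It means that the size is unknown and may be zero, and that dropping the code outright could lose real insulin users. It does not clear the code. An ambiguous label that counts as a case on one record is a defect in what the protocol fixes, and the protocol contains no step that resolves it. Differences between the countries that already exist are no reason to leave another that can be removed cheaply.

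A reader might infer that the UK off-label proportion is inflated, or that a Denmark–UK difference in insulin co-use would be an artefact of the code list. The documents support neither, because they give no content or frequency for the code.

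**Conclusion.** The point holds as a minor code-list defect. By its label, 16221 does not establish that a prescription was for insulin, yet under the one-prescription rule it can alone make a UK user an off-label case, with no Danish equivalent. False cases arising this way could only raise the UK insulin co-use count. That is a statement about this one source of error, not about the net bias of the reported proportion.

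The size cannot be determined from the protocol and may be nil. Each 1% of about 20,000 UK users affected would add about 200 cases, or one percentage point. This rests on two conditions: that oral products are filed under 16221, and that the users concerned have no other insulin record in the window. Neither is shown.

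**What to change.** Do not let 16221 count as insulin on its own. Before the off-label analysis:

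1. Extract all 16221 records that fall between a user's first and last rosiglitazone prescriptions.
2. Resolve each by the drug formulation that section 6.2 says is held in the GPRD Drug File, and count it only when the product is insulin.
3. Report the UK insulin co-use proportion with and without any records that cannot be resolved.
4. Add a line to Appendix 1 stating this rule.

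Keep the code in the extraction rather than deleting it, since it may hold true insulin prescriptions. The cost is a small look-up in data the study already plans to use, with no change to the design or to the Danish analysis. If no oral products are found under the code, one sentence in the report closes the matter.
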